The study will take place in the department of Gynecology and Obstetrics of Hvidovre University Hospital, Copenhagen Denmark in the period of May 2019 to May 2020. Inclusion criteria for the study cohort and controls will be patients i. referred from specialist gynecologists or GPs with SUI; ii. speak and understand Danish; iii. has a voiding diary that indicates stress incontinence; iv. older than 18 years of age; vii. with BMI under 35; viii. and present with mild to severe SUI evaluated after ICIQ-SF (slight (1-5), moderate (6-12), severe (13-18) and very severe (19-21), Kloving 2009). Exclusion criteria presence of pelvic organ prolapse greater than stage II by the POP-Q system, previous pelvic surgery, current infections, keloid formation, vaginal pain, dyspareunia and ongoing pregnancy.

Interventions

In this study, women will receive a series of three treatments using a fractional (pulsed) CO₂ laser system (SmartXide² MonaLisa Touch, DEKA M.E.L.A Srl, Florence, Italy), each performed in an outpatient setting without analgesia. A tubular laser-probe is inserted in the vaginal canal until reaching the vaginal vault. A burst of laser pulses is transmitted through the probe and deflected at 90° in four directions towards the vaginal wall, then rotated 45° for a second burst of pulses. Guided by markings on the probe, it is withdrawn

4mm and the procedure is repeated until reaching the introitus. Treatment parameters include power 30W, dwell time 1000 μ s, 1000 μ m spacing, using normal scan mode, with Smartstack setting for 1 at first application and 3 for the next two applications.

Both study- and placebo- treatments will be performed by specialist gynecologists employed in the department. Patients, who meet inclusion criteria and consent to study participation, will be randomized by computer service [REF] to conservative treatment, which encompass local estrogens (Vagifem 10 μ g twice weekly) if relevant (postmenopausal women) and pelvic floor training supervised by specialised physiotherapists in our own institution, whilst the study cohort will receive the same treatment with the addition of transvaginal laser applied thrice with 25- 45 days apart (CO₂ laser- treatment (DEKA SmartXide² Laser System, MonaLisa Touch). The controls will receive placebo treatment, with the use of the inactive laser, but relevant sound effects.

Outcomes

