Primary outcome of the study is patient experienced improvement of SUI evaluated by standardized ICIQ-SF questionnaire.

Our secondary outcome is objective improvement as measured by standardized stress test performed by specialist nurse before treatment and 1-2 month after last laser or placebo treatment. The bladder is emptied with a catheter and 300ml of saline is inserted. The patient is then stood up wearing a pad with legs slightly apart and asked to forcefully cough 3 timers. The examiner registers whether there is incontinence as either yes or no as well as grams of urine leakage in the pad. Furthermore, side- effects both positive and negative as well as patient satisfaction will be registered by the use of patient questionnaires at 1-2 months post treatment.

Participant timeline

Timeline after inclusion

- 1st visit in outpatient clinic: evaluation by nurse or physician; instruction in minimal care treatment, pelvic examination, evaluation of bladder diary, evaluation of study eligibility and randomization. Baseline information registered in case report form and referral to physiotherapy.
- 2nd visit. 1st Laser/placebo treatment
- 3rd visit 2nd Laser/placebo treatment (between 20 and 40 days after previous treatment)
- 4th visit 3rd Laser/placebo treatment (between 20 and 40 days after previous treatment)
- 5th visit. Follow up 1-2 months after last treatment. ICIQ-SF questionnaires, clinical examination and standardized stress test. Information registered in case report form.

Both study-cohort and controls will receive pelvic floor training supervised by specialised physiotherapists. If the treatment is evaluated as unsuccessful, next treatment option will be considered.

4. Sample size

Based on variation and observed effect of more than 2 points from other studies (Blagajna 2018) on the ICIQ-UI SF scale we have calculated that 20 patients in each group would be sufficient even with 20% dropout to show a difference. The assumptions are significance level of 0,05 and a risk of type 2 error set to 20%.

Recruitment

All urogynecologist and specialised urogynecological nurses at the department will be actively involved in the study and will be actively including patients.

Methods: Assignment of interventions (for controlled trials)

Sequence generation

A computer will generate the numbers using blocks of 6.

Allocation concealment mechanism

Allocation will be hidden in a computer program.

Implementation

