The data manager will do the sequence generation. Doctors at the urogynecological clinical will enroll patients and assignment will occur when patient data is submitted in the electronical case report form.

Blinding (masking)

The patient and the outcome assessor (nurse) will be blinded. However, the doctor performing the laser treatment cannot be blinded.

Unblinding will occur if a patient suffers adverse events that requires treatment or exclusion of the trial.

Methods: Data collection, management, and analysis

Data collection methods

Baseline data will be recorded: age, BMI, parity, ICIQ-UI SF, standardized stress test, degree of pelvic prolapse. All data will be saved in RedCAP, which will provide facilities for randomization as well as ensure that data are being stored according to Danish legislation.

ICIQ-UI SF is a validated scale for measuring degree of stress incontinence and has been used in many studies.

Data collection forms will be constructed in RedCap.

Both the study cohort and controls will be contacted by telephone, if they do not come for follow-up treatment or data-collection.

Nurses will be instructed in the standardized stress test.

Statistical methods

The post treatment scores will be compared using Students t-test for the primary outcome and chi square test for dichotomous outcomes. Our strategy is an intention to treat analysis when possible. Clinically significant differences of our primary outcome is probably at least 2 points.

Methods: Monitoring (6)

Data monitoring

All investigators will be part of the monitoring board and will decide whether the trial should be terminated. No interim analysis are planned due to the few patients involved.

Harms

All harms will be reported verbatim. Serious adverse events will be discussed by the monitoring board within two work days.

Auditing

No auditing is planned as the procedures and measurements will be carried out by very few health workers.

Ethics and dissemination

Research ethics approval

Relevant approvals from ethics committee and data protection agency will be obtained.

Protocol amendments

Protocol amendments will be reported to ethics committees and trial registries.

Consent or assent (12)

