Written and oral consent will be obtained and documented recruiting gynaecologist or specialized nurse in the outpatient clinic. At the clinic patients are attended individually in a separate room. If they are interested they will be scheduled for treatment. In the mean time they can consult with their doctor or family.

Confidentiality

Data will be collected, stored and reported in accordance with Danish legislation and approval from the data protection agency will be obtained.

Declaration of interests

All investigators will have to provide a declaration of interest before the study begins. Investigators with conflicts to the manufacturer of the Laser device will not be able to participate in this study.

Access to data

Only investigators will have access to data. Data will either be anonymized or destroyed a few years after the study finishes.

Ancillary and post-trial care (11, 15)

As this treatment is already being used in Denmark, patients that suffer damage will be eligible to compensation through the 'Patienterstatningen'.

No participation fee for participant will be given.

Dissemination policy (13)

Results will be reported in peer reviews journals and the study results will be registered at clinicaltrials.gov.

Professional writes will not be used. We will share our data to the extent it does not interfere with privacy and Danish legislation.

Economy (10)

Hvidovre hospital has so far funded the project with 60.000. The project has been initiated by the authors of the protocol. Additional funding will be sought to employ a PhD student for managing data, doing analyses and writing the paper. The department will pay for salary of the nurses and treating physicians and the Laser is already at our institution.

Additional information to Danish ethics committee

7. Biological material

No biological material will be collected

8. Information from patient charts

We will ask patients permission to look up weight, height, medicine and prior illnesses from their chart. We will also ask permission to look up admission 12 months following last treatment. This is required to monitor adverse events.

9. Handling of patient information

All patient data will be safely stored in accordance with Danish legislation. Approval from the data protection agency will be obtained.

14. Research ethics

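### Randomisation is placed at visit 1, before the time offered for reflection, so women who withdraw before session 1 are already randomised in a 40-woman trial

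*Protocol*

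**What the plan says.** Four places in the Protocol bear on the order of events.

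- **Participant timeline.** Visit 1 includes "evaluation of bladder diary, evaluation of study eligibility and randomization", followed by "Baseline information registered in case report form and referral to physiotherapy". Treatment starts at the next visit: "2nd visit. 1st Laser/placebo treatment". Intervals are given between treatment sessions, but none between visits 1 and 2.
- **Implementation.** "assignment will occur when patient data is submitted in the electronical case report form". Baseline data are registered at visit 1, so this fits allocation on that day.
- **Consent or assent.** "If they are interested they will be scheduled for treatment. In the mean time they can consult with their doctor or family". No visit number and no signing date are given.
- **Interventions.** "Patients, who meet inclusion criteria and consent to study participation, will be randomized by computer service". Consent therefore comes first, again without a date.

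The sample size section states that "20 patients in each group would be sufficient even with 20% dropout to show a difference". The statistical methods section plans an intention-to-treat analysis, qualified as applying where it is possible.

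**The concern.** The consent section ties the time to consult to the wait for treatment. The timeline has already randomised the woman by then. If she decides against taking part during that wait, she counts as randomised although she has received neither laser nor sham.

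The Protocol does not say how she would be handled. Leaving her out departs from strict intention to treat and reduces the number analysed. Following her up untreated keeps the randomised set but shrinks the contrast between arms. Either way, a loss that could have occurred before randomisation occurs after it, in a trial with 20 women per arm and little slack.

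The early allocation also serves no stated purpose. Both arms get the same conservative care and supervised pelvic floor training, so no procedure before visit 2 depends on the arm.

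**Working it through.** **Order of events**

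1. Visit 1: eligibility, baseline registration, randomisation, physiotherapy referral (Participant timeline).
2. Assignment on submission of the electronic case report form (Implementation).
3. Interval of unstated length, in which the woman may consult others (Consent or assent).
4. Visit 2: first laser or sham session (Participant timeline).

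Consent must precede the randomisation in step 1 (Interventions). So either consent is signed before the reflection time is over, or the visit at which randomisation occurs is misplaced. The text does not say which.

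**Inputs for the size**

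- 20 per arm, 20% dropout: 20 × 0.8 = 16 per arm evaluable.
- "significance level of 0,05 and a risk of type 2 error set to 20"%, that is, 80% power. Sidedness is not stated; two-sided is assumed.
- Difference of 2 points on the ICIQ-UI SF (sample size and statistical methods sections).
- SD: not stated. Two assumed values are used. SD 2.0 is compatible with the planned size. SD 2.6 is the follow-up SD of the small YAG cohort described in the introduction (12.0 ± 1.8 falling to 5.6 ± 2.6).
- Share withdrawing between visits 1 and 2: not stated. Assumed 2 of 20 per arm; a range of 5% to 20% would be 1 to 4 women per arm.

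**The plan's own figure**

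n per arm = 2 × SD² × (1.96 + 0.84)² / difference². With SD 2.0 this is 2 × 4 × 7.85 / 4 = 15.7, rounded up to 16, and 16 / 0.8 = 20. The stated 20 is therefore compatible with an SD of about 2.0. This is not a reproduction, because the SD was chosen to fit.

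**Power, two-sided t-test**

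Power comes from the noncentral t distribution with 2n − 2 degrees of freedom and noncentrality difference / (SD × √(2/n)). At SD 2.0 the noncentrality is 2.83 for n = 16 and 2.65 for n = 14.

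| Case | n per arm | Difference | Power, SD 2.0 | Power, SD 2.6 |
|---|---|---|---|---|
| Planned 20% dropout only, or withdrawals within it | 16 | 2.00 | 78.1% | 55.8% |
| 2 more lost per arm, on top of the 20% | 14 | 2.00 | 72.1% | 50.0% |
| 4 more lost per arm, on top of the 20% | 12 | 2.00 | 64.9% | 43.7% |
| 2 of the 16 analysed per arm untreated | 16 | 1.75 | 66.8% | 45.3% |

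In the last row the difference is 2 × 14/16 = 1.75, on the assumption that untreated women in both arms score like sham-treated women.

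Two extra losses per arm cost 78.1 − 72.1 = 6.0 points, or 55.8 − 50.0 = 5.8 points. The lower level in the SD 2.6 column is a separate sample-size question and is not caused by the timing of randomisation.

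**The case against.** The strongest reply is that the order is inferred. The Interventions section randomises only women who have consented. The timeline is headed as running after inclusion, so consent could already be complete. The consent section's time to consult could come before signature, or could simply describe the continuing freedom to withdraw. This stands in part: the documents do not show that anyone is randomised without consent, and a reader should not infer it. But eligibility is evaluated at visit 1 under that same heading, so the heading does not settle the matter.

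Three stronger readings are tempting and not supported.

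- **Bias between arms.** Patients are blinded and both arms follow the same schedule, so withdrawal before session 1 should not depend on the arm. Omitting such women departs from strict intention to treat but does not by itself bias the comparison.
- **Unblinding of the assessor.** Visit 1 may be run by a nurse, and a nurse performs the stress test. But the Protocol hides allocation in a computer program, and nothing says that the assessing nurse sees it.
- **A certain loss of power.** The 20% dropout allowance is not restricted to losses after treatment begins. Withdrawals within it cost nothing relative to plan, although they use up margin. Non-attenders are to be telephoned, so some who decline treatment may still give outcome data.

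Moving randomisation also has a drawback: if the unblinded operator triggers it, at one site with fixed blocks of 6, upcoming allocations become more predictable.

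**Conclusion.** The point holds as an avoidable weakness in sequencing. The timeline randomises at visit 1, the reflection time is tied to the wait for treatment, and the date of signed consent is missing. A woman who withdraws in between is already randomised, and her handling is left open.

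The harm is modest: about 6 percentage points of power if 2 of 20 per arm are lost beyond the 20% allowance, at either SD. It is about 11 points (78.1 − 66.8, or 55.8 − 45.3 = 10.5) if 2 of 16 are analysed untreated, and nil relative to plan if the losses fall within the allowance. The withdrawal share and both SDs are assumptions. The change is worth making because it costs almost nothing and nothing described before visit 2 needs the allocation.

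**What to change.** Delete the reference to randomisation from the visit 1 entry, and state that:

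- eligibility and enrolment are fixed at visit 1;
- randomisation takes place in REDCap at visit 2, immediately before session 1, after the reflection time and signed consent, and once the baseline ICIQ-SF and stress test are locked;
- the timing of the baseline relative to the start of physiotherapy is the same for all women;
- someone other than the assessing nurse, and preferably not the operator, triggers the allocation, and it is hidden from that nurse.

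Reconcile the Interventions, Participant timeline, Implementation and Consent sections with this, including the date on which consent is signed.

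The cost is Protocol wording and a REDCap user-rights setting. Two small downsides remain: the device mode has to be set on the day, and physiotherapy common to both arms may begin before randomisation. The latter is why the baseline timing has to be fixed.

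### Visit 5 is dated from the last treatment, so women who stop early have no clear or comparable outcome date and women who never start have none

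*Protocol*

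**What the plan says.** In the protocol's Participant timeline, eligibility, randomisation and the start of background care all fall at visit 1: "Baseline information registered in case report form and referral to physiotherapy". The next step is "2nd visit. 1st Laser/placebo treatment", with no limit on the wait since visit 1. Sessions two and three follow at stated intervals, for example "3rd visit 2nd Laser/placebo treatment (between 20 and 40 days after previous treatment". The outcome visit is then "5th visit. Follow up 1-2 months after last treatment. ICIQ-SF questionnaires, clinical examination and standardized stress test".

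The Outcomes section uses the same kind of anchor. The stress test is done "before treatment and 1-2 month after last laser or placebo treatment", and "patient satisfaction will be registered by the use of patient questionnaires at 1-2 months post treatment". No outcome is timed from randomisation.

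Three other statements bear on the point:
- On background care, the timeline says: "Both study-cohort and controls will receive pelvic floor training supervised by specialised physiotherapists".
- On analysis, Statistical methods compares post-treatment scores with a t-test and adds: "Our strategy is an intention to treat analysis when possible".
- On missed visits, Data collection methods says that women in both arms who miss treatment or data collection will be telephoned. It attaches no assessment date to that call.

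**The concern.** How many sessions a woman attends, and when, is settled after randomisation. An outcome dated from the last session therefore has no fixed place in time for a woman who leaves the schedule, and a woman who has no session has nothing to date it from.

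Elapsed time may matter because both arms are referred to supervised pelvic floor training. The protocol's Introduction cites a review in which 59% of women with stress incontinence were cured after 12 months of such training. A woman scored early may have had less time to benefit, and the planned t-test has no term for time.

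Two things are at stake. Women who leave treatment may have no outcome, or one taken at a different time, although the plan is to analyse by intention to treat. And if more women stop in one arm than in the other, the difference in timing would enter the comparison between arms.

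**Working it through.** The protocol gives no figure for the time from randomisation or first session to visit 5, so there is none to reproduce. It can be built from the schedule.

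**Inputs.** Session interval 20-40 days (Participant timeline) or 25-45 days (Interventions). Follow-up 1-2 months, taken as 30-61 days.

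**Reading A: the anchor is the last session received.** Days from session 1 to visit 5 after k sessions = (k - 1) × interval + follow-up.

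| Sessions received | 20-40 day interval | 25-45 day interval |
|---|---|---|
| 1 | 30 to 61 | 30 to 61 |
| 2 | 20 + 30 = 50 to 40 + 61 = 101 | 25 + 30 = 55 to 45 + 61 = 106 |
| 3 | 2 × 20 + 30 = 70 to 2 × 40 + 61 = 141 | 2 × 25 + 30 = 80 to 2 × 45 + 61 = 151 |
| 0 | no date | no date |

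For the same follow-up gap, a woman who stops after session 1 is assessed 40-80 days sooner than a completer (50-90 days with the other interval).

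**Reading B: the anchor is the third session.** Nobody is assessed early, but women with zero, one or two sessions all lack a due date.

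**What early assessment could do to the score (Reading A only).** The protocol gives neither an early-stopping rate nor a time course for improvement, so these are assumptions:
- Background gain of 2-6 ICIQ points, accruing linearly and complete at the completers' mid-value.
- Mid-values of a 30-day interval and 45-day follow-up: 45 days after one session, 30 + 45 = 75 after two, 60 + 45 = 105 after three.

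Share of the gain missed by a session-1 stopper: (105 - 45)/105 = 57%. In points: 0.57 × 2 = 1.1 to 0.57 × 6 = 3.4.

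If one arm has one more such woman in 20 than the other, the group difference shifts by 1.14/20 = 0.06 to 3.43/20 = 0.17 points. Against the 2 points that Statistical methods treats as probably clinically significant, that is 3-9%.

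**Sensitivity to the wait before session 1.** Referral to physiotherapy is at visit 1, so the clock may start earlier. With an assumed wait of 30 days the share missed is 60/135 = 44%; with 60 days it is 60/165 = 36%. The shift for one extra stopper becomes 0.04-0.13 or 0.04-0.11 points.

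**The case against.** Several counter-arguments have force.

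- **The natural reading may be the third session.** The visits are numbered, visit 4 is the third treatment and visit 5 follows it. On that reading no one is assessed early, and the arithmetic on points falls away. This stands. It does not clear the plan, because early stoppers then have no date at all.
- **A reader might infer that the comparison is biased.** The documents do not support that. Both arms have the same visits, the sham has sound effects and patients are blinded. The Introduction reports no serious complications in the cited laser studies. Active energy without analgesia and unblinded treating doctors make different stopping rates possible, but nothing shows that they will occur.
- **A reader might compute a much larger shift.** If 20% of one arm and none of the other stopped after session 1 and all attended visit 5, the method above gives 0.23-0.69 points, or 11-34% of 2 points. That split is extreme: the 20% in the Sample size section is overall dropout, not a difference between arms, and may include women with no outcome. The linear gain has no source in the protocol, which also does not say when training starts or how long it lasts.
- **Intention to treat means analysing women as randomised, not at one calendar time.** This is correct. But the analysis still needs an outcome for each woman, and the schedule gives some of them no date for one.
- **Timing from the end of a course is legitimate.** This also stands, and it argues against moving everyone to a fixed week from randomisation. For example, week 20 plus or minus 2 is day 126-154. With no wait before session 1, session 3 falls on day 40-80, so completers would be seen 126 - 80 = 46 to 154 - 40 = 114 days after it. That is a 68-day spread against 31 now, mostly outside the protocol's 1-2 months. With a 60-day wait, session 3 falls on day 100-140, and visit 5 could precede it.

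**Conclusion.** The point holds in a limited form. Without any assumption, the protocol gives a never-treated woman no outcome date. It gives an early stopper either a date about 40-80 days sooner than a completer's (stopping after session 1, 20-40 day intervals) or no date, depending on how the anchor is read. That weakens the stated intention-to-treat comparison.

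Bias between arms is a possibility, conditional on stopping that differs by arm. Its size is unknown; the 0.06-0.17 points for one extra stopper in 20 only illustrates scale, and only under the reading that anchors on the last session received. The text does not support a statement that the trial's result is biased, or that every early stopper will be assessed early.

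This is not something to leave to an analysis plan: the visit schedule is fixed in the protocol, and an assessment that was never scheduled cannot be recovered at analysis. It is a cheap improvement worth making, not a defect that invalidates the design.

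**What to change.** In Outcomes and Participant timeline:

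1. State that completers have visit 5 at 1-2 months after session 3, as now. Do not move them to a fixed week from randomisation.
2. At randomisation, book the planned dates of all visits, including the first session.
3. State that any woman who stops early or never starts, in either arm, has the ICIQ-SF and stress test on the date her visit 5 would have fallen under that planned schedule. Use the existing telephone contact to arrange it.
4. Reconcile the session intervals (25-45 days in Interventions, 20-40 days in Participant timeline), since the planned date cannot be set while they disagree.

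The cost is a few sentences and a booking rule, with no extra visit. The small downside is the effort of recalling women who have stopped treatment.

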A novel minimal-invasive method of treating UI, has been introduced in the recent years, namely vaginal laser treatment. The use of laser has now been described in pelvic organ prolapse, UI and genito-urinary symptoms of menopause. Bhide et al have recently published a review article, where they describe 5 prospective cohort studies of laser-treatment of SUI (Table 1) (Bhide AA, *Int. Urogyn. Journ.*, 2018). Gambacciani et al. published a study of 45 women with IU, of whom 19 had SUI (Gambacciani M, *Ital J Gynaecol Obstet*. 2015). Vaginal treatment included application of YAG laser 3 times with 1 month apart and symptoms were evaluated at baseline and at a 3- and 6-month follow-up with ICIQ-U1 SF questionnaire. The treatment induced a significant decrease in ICIQ-U1 at 3 months with decrease of ICIQ scores from 12.0+/- 1.8 to 5.6+/-2.6 and this was still significant at 6 months. Ogrinc et al published a study on the use of YAG laser on women with IU, of whom 115 had SUI. Symptoms were evaluated at baseline and at 12-months follow-up with Incontinence Severity Index (ISI) and all women showed significantly decreased ISI scores (Ogrinc UB, *Lasers Surg Med*. 2015). Fistonic et al published two studies of the use of a single application of YAG laser in the treatment of SUI and evaluated with ICIQ-U1 SF. The first study evaluated 31 women with SUI and follow-up at 1- 2- and 6- months showed significantly reduced ICIQ-IU SF scores albeit many of women were lost to follow-up (Fistonić N., *YAG. Lasers Med. Sci.* 2016). The next study of 73 women with SUI showed 72.3% experiencing improvement of symptoms, 23.4% experiencing no change and 4.3% experiencing worsening (Fistonić N, *Climacteric*. 2015). Pardo et al. evaluated the vaginal erbium:YAG laser in a longitudinal prospective study in 42 patients with SUI (Pardo JI, *Eur J Obstet Gynecol Reprod Biol*. 2016). Treatment was applied twice with 21- 28 days apart and median ICIQ-IU SF scores, which was reported at 3- and 6- months follow-up, was significantly reduced; 78.6% reported improvement of SUI and 38.1% reported a complete remission of SUI. Gambacciani et al. studied 205 post-menopausal women of which 114 were diagnosed with SUI. In this study, three vaginal erbium:YAG laser applications were administered at 30-day intervals, and ICIQ-SF was used to evaluate before and after treatment with follow-up up to 24 months post treatment (Gambacciani M, *Climacteric*. 2018). The results demonstrated a significant decrease in ICIQ-SF scores from baseline to 12 months post treatment. However, at 18 and 24 months, ICIQ-SF scores were not significantly different from baseline. All 5 studies used a non-randomised selection of patients and treatment effect was estimated by using pre-treatment incontinence scores for comparison . Only the YAG laser has been evaluated in a randomized trial with 114 women which found significant improvement in the ICIQ-SF scores in the treatment arm compared with placebo (Bleganje 2018). None of the mentioned studies showed any serious complications or side effects of the laser treatment.

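### The primary t-test ignores the baseline ICIQ-UI SF score that the trial already records; using it as a covariate would gain precision at almost no cost

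*Protocol*

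**What the plan says.** - **Primary analysis** (Protocol, Statistical methods): "The post treatment scores will be compared using Students t-test for the primary outcome". No covariate is named. The same section adds: "Clinically significant differences of our primary outcome is probably at least 2 points".
- **Baseline data** (Protocol, Data collection methods): "Baseline data will be recorded: age, BMI, parity, ICIQ-UI SF, standardized stress test, degree of pelvic prolapse". The outcome scale is therefore measured before treatment as part of the standard data set.
- **Size** (Protocol, 4. Sample size): "20 patients in each group would be sufficient even with 20% dropout to show a difference". The stated basis is "Based on variation and observed effect of more than 2 points from other studies", with one cited randomised trial as the source, and "The assumptions are significance level of 0,05 and a risk of type 2 error set to 20" per cent. No SD, exact effect or sidedness is printed there or elsewhere in the protocol.

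**The concern.** The ICIQ-UI SF score before treatment will usually predict the score after it. An unadjusted comparison leaves that predictable variation between women in the error term. In a large trial this might matter little. Here 20 women per arm, less 20% dropout, leaves 16, and a wider error term costs both power and width of the confidence interval. The interval matters because the protocol names 2 points as the probable threshold of clinical relevance. After a non-significant result, the half-width of the interval decides whether 2 points can be excluded.

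The stated method also gives no protection against a chance difference between the arms in baseline severity, which is more likely to be noticeable in a trial of this size.

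**Working it through.** **Inputs from the protocol.** Alpha 0.05; type 2 error 20%; 20 per arm; dropout 20%, so 20 × 0.8 = 16 evaluable per arm; relevant difference 2 points.

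**Assumptions.** The test is two-sided. The SD of the post-treatment score is 2.0 or 2.6, and the correlation r between baseline and post-treatment score runs from 0 to 0.7. The documents give no planning value for either. SD 2.0 is the round value that recovers the protocol's N (step 1). The 2.6 is the post-treatment spread in the Introduction ("decrease of ICIQ scores from 12.0+/- 1.8 to 5.6+/-2.6"). It is not labelled as an SD and comes from an uncontrolled study of another laser with 19 women with stress incontinence, so it serves only as an illustration.

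**Step 1: can the protocol's 20 per arm be recovered?** Not forward, because the SD and the exact effect are missing. Backward, with 2 points and SD 2.0 in the normal formula:

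n = 2 × (1.960 + 0.842)² × (2.0/2)² = 15.7, so 16; and 16/0.8 = 20.

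The printed figure is thus consistent with an ordinary calculation.

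**Step 2: power of the stated t-test for 2 points.** The noncentrality is 2 / (SD × √(2/16)), with 30 df.
- SD 2.0: noncentrality 2.83, power 78%.
- SD 2.6: noncentrality 2.18, power 56%.

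**Step 3: the same with baseline as covariate.** The residual SD is SD × √(1 − r²), with 29 df. At r = 0.5 the factor is √0.75 = 0.866, so the residual SD is 1.73 (from 2.0) or 2.25 (from 2.6).

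| r | Power, SD 2.0 | Power, SD 2.6 |
|---|---|---|
| unadjusted t-test | 78% | 56% |
| 0.3 | 82% | 60% |
| 0.5 | 88% | 68% |
| 0.6 | 93% | 75% |
| 0.7 | 97% | 84% |

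The correlation needed for 80% power is 0.22 at SD 2.0 and 0.66 at SD 2.6.

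**Step 4: confidence interval half-width.** This is t × residual SD × √(2/16), with t = 2.042 (30 df) or 2.045 (29 df). Going from unadjusted to adjusted at r = 0.5, it falls from 1.44 to 1.25 points at SD 2.0, and from 1.88 to 1.63 at SD 2.6.

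**Step 5: the price if baseline predicts nothing.** At r = 0 and SD 2.6, losing one degree of freedom moves power from 55.8% to 55.7%. Step 3 takes the arms as balanced at baseline. Chance imbalance multiplies the variance of the adjusted difference by 1 + t²/30, where t is the baseline t statistic on 30 df; on average this is 1 + 1/28 = 1.036. Averaged over that distribution, power at r = 0.5 is 87% and 67% instead of 88% and 68%. At r = 0 it is 77% and 54% against 78% and 56% unadjusted. The worst case is a loss of about 1.5 percentage points.

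**Step 6: the SD that the sample size needs.** For exactly 2 points at 80% power and 16 per arm, two-sided, the SD may be at most 1.95 (t-test) or 2.02 (normal formula). With the t-test this rises to 2.22 if the test is one-sided, or 2.20 if all 20 per arm are evaluable.

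**The case against.** An unadjusted t-test is valid in a randomised trial, so nothing here biases the result, and the size of the gain rests on correlations that the documents do not give. Both points stand: this is a matter of efficiency, and the table is a range, not a forecast. It can also be said that covariates are commonly left to an analysis plan. That would answer a protocol that was silent, but this one names the test for its primary outcome, and any later plan would have to depart from it.

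A reader might go further and infer from the unprinted SD that the trial is too small. The documents do not support that.
- The plan rests on an effect of more than 2 points, and a larger effect tolerates a larger SD: at SD 2.6, about 2.66 points gives 80% power.
- The 80% limit near SD 2.0 holds only for a two-sided test, the full 20% dropout and exactly 2 points.
- The printed spreads of 1.8 and 2.6 are not planning values for this trial.
- The wide entry range of ICIQ scores does not determine how far post-treatment scores will spread.
- An SD of 2.0 reproduces 20 per group exactly.

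**Conclusion.** The point holds as an improvement to the stated primary analysis. The protocol fixes a less precise method than its own data allow, in a trial where precision is scarce. If the correlation is 0.5, the gain in power for 2 points is about 10 to 12 percentage points over SDs of 2.0 to 2.6, and the confidence interval is about 13% narrower (√0.75 = 0.866). If the correlation is near zero, the loss is about 1.5 percentage points at most. These figures assume a two-sided 0.05 test, 16 evaluable women per arm and a linear relation between the two scores.

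The missing SD, exact effect and sidedness are a reporting gap of second rank. They prevent a check of the calculation but do not show that its result is wrong.

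**What to change.** In Statistical methods, replace the t-test for the primary outcome by wording such as: *The post-treatment ICIQ-UI SF score will be analysed in a linear model (ANCOVA) with treatment arm and baseline ICIQ-UI SF score as explanatory variables. The adjusted difference between arms will be reported with its two-sided 95% confidence interval and interpreted against a difference of 2 points.* The unadjusted comparison can stay as a supporting analysis.

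As a reporting note in the sample-size section, print the SD and effect taken from the cited trial, and state whether the test is two-sided. The spreads of 1.8 and 2.6 from the Introduction should not be written in as planning SDs.

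The cost is two short text changes and one degree of freedom in the analysis. N, visits and data collection stay as they are.
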